17.1 Adverse Events

Adverse Events will be coded using latest version of MedDRA at the end of each of 2 reporting periods (2 year and 5 year analyses).

For 2 years analysis: Treatment-emergent adverse events (TEAEs) are defined as those adverse events that either start or worsen in severity on or after the date of first dose of study treatment (first injection) until 30 days from last dose of study treatment (last injection). Where dates are missing or partially missing, adverse events will be assumed to be treatment-emergent, unless there is clear evidence (through comparison of partial dates) to suggest that the adverse event started prior to the first dose of study treatment or after the subject's last treatment (+30 days). See appendix 20.4 for details.

For 5 years analysis: All AEs from the complete duration of the study will be summarized (but not TEAEs, as these are not relevant per definition above). There will be no summaries of TEAEs for the 5 years analysis only AE

Pre-treatment emergent adverse events, i.e. adverse events starting between date of informed consent and until date of first dose of study treatment will be tabulated separately.

Adverse events of special interest (AESI) will include the following:

Injection site reactions will be summarized by treatment group and PT. These will be identified using higher level term (HLT) "Injection site reactions".

Similarly, musculoskeletal complaints (eg. Back pain, neck pain), will be identified using prespecified SOC "Musculoskeletal and connective tissue disorders" and will be summarized by treatment group and by PT.

In addition, Neoplasms will be identified using pre-specified SOC "Neoplasms benign, malignant and unspecified (including cysts and polyps)" and will be summarized by treatment group and by PT.

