In the DBPC treatment phase, all subjects will receive 4 cycles of treatment with the IMP (sprifermin or matching placebo) at intervals of 6 months. Each cycle will consist of 3 once-weekly i.a. injections over a period of 3 consecutive weeks.

The DBPC treatment phase will begin at the baseline visit (Week 0/Visit 2), when eligibility will be confirmed, subjects will be randomized, and the first IMP injection will be administered.

Subjects will be randomized in equal allocation to one of the following treatment groups, as shown in [Figure 1](#) (randomization is described in Section 6.3).

- 4 cycles of sprifermin (100 mcg per injection)
- 2 cycles of sprifermin (100 mcg per injection) alternating with 2 cycles of placebo
- 4 cycles of sprifermin (30 mcg per injection)
- 2 cycles of sprifermin (30 mcg per injection) alternating with 2 cycles of placebo
- 4 cycles of placebo

The last of the four cycles of 3 injections of IMP will be given on Week 78/Visit 17, and the last dose of IMP is scheduled to be administered at Week 80/Visit 19. IMP administration for each treatment group is summarized in [Table 1](#), Section 6.2.

Major efficacy assessments will take place at intervals of 6 months, on the first day of each treatment cycle and at the end of the DBPC treatment phase (Week 104/Visit 22).

Minor efficacy assessments will also take place at intervals of 6 months, occurring 9 weeks after the end of each treatment cycle.

Details of DBPC treatment phase visits are presented in Section 7.1.3.

Efficacy assessments will include MRI and X-ray of the target knee, the WOMAC, the 20-meter walk test, and the Patient's Global Assessment of disease impact (PGA). The Knee Injury and Osteoarthritis Outcome Score QOL subscale (KOOS QOL) and the Medical Outcomes Study Short Form-36 General Health Survey (MOS SF-36) will be assessed for exploratory analysis of treatment effect on health-related QOL. The NRS will be used to explore treatment effect on worst pain in the past 24 hours in the target knee. The Measure of Intermittent and Constant Osteoarthritis Pain (ICOAP) and the KOOS Symptom Index questionnaires will be used to explore treatment effect on OA-related symptomatology in the target knee. The NRS pain scale

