7.1.3 Double-Blind Placebo-Controlled Treatment Phase (Visits 2 to 22)

The duration of the DBPC treatment phase will be 2 years (104 weeks). Trial visits during this phase are outlined in [Table 2](#), and details of the procedures to be performed are presented in [Appendix E](#).

Table 2 Trial Visits during DBPC Treatment Phase

Visit Number	Week*	Treatment	Visit Name or Type
2	0	X	Baseline – Major Efficacy
3	1	X	
4	2	X	
5	3		
6	12		Minor Efficacy
7	26	X	Major Efficacy
8	27	X	
9	28	X	
10	29		
11	38		Minor Efficacy
12	52	X	Major Efficacy
13	53	X	
14	54	X	
15	55		
16	64		Minor Efficacy
17	78	X	Major Efficacy
18	79	X	
19	80	X	
20	81		
21	90		Minor Efficacy
22	104		Major Efficacy

* Relative to randomization and initiation of therapy at Week 0. Assessments performed at “major” and “minor” efficacy visits are described in Sections 7.1.3.3 and 7.1.3.4 respectively.

Subject eligibility for the trial will be confirmed at the baseline visit (Week 0/Visit 2; see Section 7.1.3.1) based on scores for Question 1 of the WOMAC pain index at screening and baseline (see Section 5.4). Eligible subjects will then be randomized and the first i.a. injection of IMP will be administered.

I.a. injections of the IMP will be administered at the baseline visit (Week 0/Visit 2) and at the visits identified in Section 7.1.3.2.

Major efficacy assessments will take place at intervals of 6 months, at the beginning of each treatment cycle and at the end of the DBPC treatment phase (Week 104/Visit 22; see Section 7.1.3.3).

Minor efficacy assessments will also take place at intervals of 6 months, occurring 9 weeks after the end of each treatment cycle (see Section 7.1.3.4).

Subjects will be requested to discontinue the intake of all pain medications for 5 half-lives before a visit involving completion of the WOMAC (see Sections 5.4 and 7.1.2). At least 3 days before each such visit, subjects will be contacted by phone to remind them of this requirement. When

the upcoming visit includes injection of IMP, this phone contact will include a reminder to complete trial diary information about target knee pain and swelling for the day before the visit.

Vital signs measurement (see Section 7.4.4) and review of AEs and concomitant medications (see Sections 7.4.1 and 6.5) will be performed at all DBPC treatment phase visits.

For women of childbearing potential, urine pregnancy tests will be performed before dosing on each treatment day (see Section 7.1.3.3).

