8.5.4 Safety Analyses

Safety data will be summarized descriptively overall and by treatment group, using the Safety Analysis Set.

AEs will be coded using the latest available version of the Medical Dictionary for Regulatory Activities (MedDRA).

All local and systemic AEs will be reported overall, by severity, and by relationship to trial drug, and summaries will be prepared of events leading to discontinuation and events leading to death.

The incidence of protocol-defined AIRs and the incidence of surgical procedures occurring to the target knee during the trial will be tabulated separately.

Laboratory safety parameters and vital signs will be descriptively summarized as appropriate.

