8.1 Analysis of data from DBPC treatment phase

An overview of endpoints and type of analysis for the DBPC treatment phase is provided in Section 19.1. The analysis will report all data collected from the DBPC treatment phase up to 24 months (day 819), i.e. disposition, demographics, baseline characteristics, concomitant medication during and prior to DBPC treatment phase, compliance and exposure, all efficacy endpoints and safety parameters up to 24 months (day 819).

Moreover, PK-related analysis will be provided by Merck Serono Quantitative Pharmacology and Drug Disposition (QPD) and Enabling Clinical Sciences (ECS) and will be incorporated in the CTR (if at least one sample show sprifermin concentration). PK analyses and biomarker subgroups (genetic markers - Single nucleotide polymorphism [SNP] and subgroups based on biochemical marker cutoffs) are included in this SAP in Section 16.3 and Section 16.4, respectively. Additional analyses of other exploratory biomarkers will be described in the BSAP and will be reported separately in an Exploratory Biomarkers Report. Any modeling of the data will be further described in a separate Modeling and Simulation SAP and will be reported in a separate Modeling and Simulation Report.

Data used for reporting of the DBPC will be the data presented in Appendix 19.1.

Upon database release, protocol deviation and Analysis Set outputs will be produced and will be sent to Merck Serono for review. A Blind Data Review Meeting will be arranged to discuss the outputs and to decide which subjects and/or subject data will be excluded from certain analyses. Decisions made regarding the exclusion of subjects and/or subject data from analyses will be made prior to breaking the blind and will be documented and approved by Merck Serono.

The blind will be kept for investigators, X-ray and MRI readers, and subjects during the follow-up phase. Individual subject data listings revealing the treatment as well as tables from the CTR will not be shared with the site investigators or X-ray or MRI readers until completion of the follow-up phase.

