^{*}treatment cycle; Day 1 is first treatment day. If multiple assessments are available within each study week window, the one closest to target day will be used. At Baseline, week 26, 52 and 78 [injections visits] pre injection assessments will be considered for the corresponding study week window). & for X-ray and this timepoint with injections - only compare to first injection in cycle # 3. don't compare to first injection in cycle #2 to determine if used in analysis or not. ~For SF36, lab, height, weight (and BMI), and pain in other joint, in the 2-years period, assessments are scheduled as qMRI, so qMRI windowing will be used. For the 2-5 years the scheduling is like ADQS, therefore, ADQS windowing will be used for these assessments.

For vital signs, which are measured at all visits, two mappings will be used, one relative to injections and one relative to target days.

Table 3a Vital signs relative to injections

Study week window	To be used relative to injection visit independent of ADY	AVISITN for injection - related ADVS
Cycle 1/Week 0/pre-injection assessment/Baseline	Yes	1
Cycle 1/Week 1/pre-injection assessment	Yes	2
Cycle 1/Week 2/pre-injection assessment	Yes	3
Cycle 1/Week 3	Yes	4
Cycle 2/Week 0/pre-injection assessment	Yes	5
Cycle 2/Week 1/pre-injection assessment	Yes	6
Cycle 2/Week 2/pre-injection assessment	Yes	7
Cycle 2/Week 3	Yes	8
Cycle 3/Week 0/pre-injection assessment	Yes	9
Cycle 3/Week 1/pre-injection assessment	Yes	10
Cycle 3/Week 2/pre-injection assessment	Yes	11
Cycle 3/Week 3	Yes	12
Cycle 4/Week 0/pre-injection assessment	Yes	13
Cycle 4/Week 1/pre-injection assessment	Yes	14
Cycle 4/Week 2/pre-injection assessment	Yes	15
Cycle 4/Week 3	Yes	16

Table 3b Vital signs relative to target days

Study week window	ADVS target day (min, max)	AVISITN for relative visit ADVS
Baseline	1 (-42, 1)	1
Month 3/Week 12	85 (2, 133)	2
Month 6/Week 26	183 (134, 224)	3
Month 9/Week 38	267 (225, 315)	4
Month 12/Week 52	365 (316, 406)	5
Month 15/Week 64	449 (407, 497)	6
Month 18/Week 78	547 (498, 588)	7
Month 21/Week 90	631 (589, 679)	8
Month 24/Week 104	729 (638, 819)	9
Month 30/Week 130	911 (820, 1001)	10
Month 36/Week 156	1093 (1002, 1183)	11
Month 42/Week 182	1275 (1184, 1365)	12
Month 48/Week 208	1457 (1366, 1547)	13
Month 54/Week 234	1639 (1548, 1729)	14
Month 60/Week 260	1821 (1730, 1849)	15
LOCF1 (up to Month 24)	Last post-baseline measurement	
	in DBPC (2, 819)	20

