17.1.1 All Adverse Events

AEs will be summarized as follows:

- Overview of all AEs
- TEAE by SOC and PT
- TEAE by severity
- TEAE by relationship
- Local TEAE by SOC and PT
- Local TEAE by severity
- Local TEAE by relationship
- Systemic TEAE by SOC and PT
- Systemic TEAE by severity
- Systemic TEAE by relationship
- Any serious adverse events (SAEs) further specified in Section 17.2.2
- Any non-serious AEs (at least 5% in any treatment group) by SOC and PT
- Most frequent TEAEs (at least 5% in any treatment group) by PT only
- Treatment emergent Injection Site Reactions by PT only (as described in Section 17.1)
- Treatment emergent Musculoskeletal disorders by PT only
- Treatment emergent Neoplasms by PT only

All AE and TEAE summaries will report the number and percentage of subjects, overall and by SOC and PT. AESI will be summarized by subjects (and %).

Each summary will be ordered alphabetically for SOC, and decreasing frequency for PT within SOC overall.

Subjects can contribute to more than one relationship or severity count per SOC/PT. In this case, the strongest relationship or worst severity will be used. If severity or relationship is missing, the worst case will be assumed.

Clinical trial.gov and EudraCT requirements: Summary table for non-serious AEs by SOC and PT (excluding SAE) with at least 5% in any treatment group will be provided.

A by-subject listing of all adverse events (including non-treatment-emergent events) will be provided. This listing will be presented by treatment group and will include: country, subject identifier, age, sex, race, target knee (left/right), adverse event (SOC, PT, and verbatim term), date of onset, date of resolution, duration, severity, seriousness, action taken, outcome and causal relationship to treatment.

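### The treatment-emergent AE tables of the 2-year analysis stop 30 days after the last injection; the local, systemic, severity, relationship and special-interest tables therefore omit 19% of the 104-week phase, and SAP section 9 does not say so

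*SAP*

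**What the plan says.** Protocol 8.5.4 commits to the following: "All local and systemic AEs will be reported overall, by severity, and by relationship to trial drug". It also promises summaries of events leading to discontinuation and to death. It sets no time limit. Protocol 7.1.3 fixes the length of the phase: "The duration of the DBPC treatment phase will be 2 years (104 weeks"). Protocol 7.4.1.3 collects AEs from consent to the end of extended follow-up.

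SAP 8.1 says the analysis of this phase covers "all efficacy endpoints and safety parameters up to 24 months (day 819").

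SAP 17.1 ends treatment-emergent status for the 2-year analysis at a point described as "until 30 days from last dose of study treatment (last injection"). Appendix 19.4 applies the rule: an event starting more than 30 days after the last dose is classed as post-treatment.

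SAP 17.1.1 then lists the local, systemic, severity and relationship tables as treatment-emergent only. The special-interest tables are treated the same way, for example "Treatment emergent Musculoskeletal disorders by PT only" and "Treatment emergent Neoplasms by PT only". SAP 17.1.2 limits the discontinuation tables likewise.

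SAP section 9, which records changes from the protocol, introduces the special-interest events but not the restriction to treatment-emergent events.

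**The concern.** The protocol's AE commitment and the SAP's own cut-off both point to the whole 2-year phase, yet the tables that classify AEs by site, severity and relationship stop well before its end.

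Two treatment-phase visits with AE review and physical examination fall after the window: Week 90 (day 631) and Week 104 (day 729). Week 104 adds MRI and X-ray. Efficacy is judged at Week 104, while harms in these tables are counted to about Week 84.

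The rule also treats like events differently. An event 10 weeks after the last injection of cycle 3 (379 + 70 = day 449) counts. The same event 10 weeks after the last injection of cycle 4 (561 + 70 = day 631) does not.

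Both documents give choosing a Phase III regimen as the main objective, so the balance of harms across groups over the full phase is part of what the 2-year report must show.

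**Working it through.** **Inputs**

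- Last planned injection (Protocol 5.1): "the last dose of IMP is scheduled to be administered at Week 80/Visit 19".
- Day numbering (SAP section 11, footnote to Table 3): "Day 1 is first treatment day".
- End of phase: Week 104, target day 729, window maximum day 819 (SAP Table 3).
- End of window: last injection + 30 days (SAP 17.1, Appendix 19.4).

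**Day scale.** Day = 7 × week + 1. For Week 104 this gives 7 × 104 + 1 = 729, as in SAP Table 3. It also reproduces the Table 3 target days for Weeks 12, 26, 38, 52, 64, 78, 90, 130 and 260.

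**Planned schedule**

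- Last injection: 7 × 80 + 1 = day 561.
- Window closes: 561 + 30 = day 591.
- Omitted to Week 104: 729 − 591 = 138 days; 138/729 = 18.9%.
- Omitted to the data cut: 819 − 591 = 228 days; 228/819 = 27.8%.

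**Effect of the permitted injection intervals.** Protocol 7.1.1 allows 21 to 27 weeks between cycles and 6 to 9 days between injections. With three between-cycle gaps and eight within-cycle gaps:

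- Earliest last injection: 1 + 3 × 147 + 8 × 6 = day 490; window closes day 520. Omitted: 209/729 = 28.7%, or 299/819 = 36.5%.
- Latest last injection: 1 + 3 × 189 + 8 × 9 = day 640; window closes day 670. Omitted: 59/729 = 8.1%, or 149/819 = 18.2%.

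**Subjects who stop injections early but stay in the trial** (permitted by Protocol 7.1.5), on the planned schedule:

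| Stops after | Last injection | Window closes | Omitted to day 729 | Omitted to day 819 |
|---|---|---|---|---|
| Cycle 1 | day 15 | day 45 | 684 (93.8%) | 774 (94.5%) |
| Cycle 2 | day 197 | day 227 | 502 (68.9%) | 592 (72.3%) |
| Cycle 3 | day 379 | day 409 | 320 (43.9%) | 410 (50.1%) |

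The documents do not say how many subjects this will be. The protocol's 30% is a drop-out assumption for the sample size, not a rate of stopping injections while remaining under observation.

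**Where a late event still appears at 2 years.** The outputs in SAP 17.1.1 and 17.2.2 not labelled treatment-emergent are the AE overview, all SAEs, non-serious AEs at or above 5% in any group, and the by-subject listing. With 109 planned per group, 5/109 = 4.6% and 6/109 = 5.5%, so a non-serious preferred term needs six subjects in one group to reach the 5% table. Below that, a late non-serious event is left to the overview and the listing.

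**The case against.** A 30-day treatment-emergent window is conventional. Protocol 8.5.1 calls its statistical section an outline and leaves detail to the SAP. The tables are descriptive. Placebo injections count as study treatment, so the planned window is the same in all five groups. All of this stands, and it is why the treatment-emergent tables should stay. It does not explain why section 9 is silent, or why no all-AE counterpart exists for the classifications the protocol names.

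It can also be argued that SAP 17.1 describes the musculoskeletal and neoplasm summaries without a window, and that an all-AE summary by system organ class and preferred term could already show them. The table shells are a separate document. But 17.1.1 labels both tables treatment-emergent, and it lists no all-AE table by class and term other than the SAE and 5% tables.

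Four stronger readings are tempting, and the documents do not support them:

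- **That late safety data are lost.** They are not. The outputs listed under the working carry late events, and the 5-year analysis summarises all AEs. A serious neoplasm after day 591 is in the table of all SAEs.
- **That 28% of the treatment phase is omitted.** The phase is 104 weeks, so its share is 19%. The 28% is relative to the day-819 cut, which lies 819 − 729 = 90 days past the Week 104 target.
- **That the protocol promised neoplasm and musculoskeletal tables.** It did not; SAP section 9 adds them. The conflict with Protocol 8.5.4 concerns local and systemic AEs, severity, relationship and discontinuation.
- **That neoplasms are expected after day 591.** The protocol's background warns of cartilage and bone growth under significant systemic exposure. It does not mention neoplasms, and it reports all measured systemic levels below the quantitation limit. Nothing in the documents dates such events.

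**Conclusion.** The point holds as a reporting gap in the 2-year analysis, not as a loss of data. On the planned schedule the treatment-emergent tables omit 138 of 729 days (19%) of the phase, or 228 of 819 days (28%) to the data cut. These figures assume all 12 injections on the planned days. Permitted intervals move the first figure between 8% and 29%, and early stoppers who remain in the trial have far larger shares.

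After the window, AEs are not tabulated by treatment group by local or systemic class, severity, relationship or special-interest category. An AE that starts later and leads to study termination is missing from the discontinuation tables. This departs from Protocol 8.5.4, does not match the day-819 scope in SAP 8.1, and is not declared in section 9.

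Whether the omission favours any group cannot be judged from the documents. The planned window is common to all groups, but it would differ between them if stopping injections early did.

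**What to change.** Keep the treatment-emergent tables. Add the same local, systemic, severity, relationship, discontinuation, neoplasm and musculoskeletal tables for all AEs with onset from the first injection to the day-819 cut. This meets Protocol 8.5.4 for local and systemic AEs and SAP 8.1 for the cut-off. Protocol 8.5.4 itself states no start or end day, so the SAP should give the period as its own choice. The injection-site table can stay as it is, since those events are tied to the injection.

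Record the restriction to treatment-emergent events in SAP section 9, with its reason.

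The data are already collected and the programs exist, so the cost is a second run of existing tables and longer output.

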One of the trial's safety endpoints is the incidence of acute inflammatory reactions (AIRs), defined as increase of pain by 30 mm on a 100 mm VAS and a self-reported synovial fluid effusion (i.e., joint swelling) within 3 days following i.a. injection. A similar definition based on a 30-mm increase in pain on VAS and observation of local swelling was used successfully in a trial in rheumatoid arthritis involving i.a. injections of interleukin-1 receptor antagonist (IL-1ra; anakinra (23)).

The extension phase of the trial will allow exploration of the drug's long-term safety.

Biomarker Assessment

Assessment of biomarkers of bone and joint tissue turnover is expected to identify candidate markers potentially predictive of response to treatment, prognostic for disease progression, or associated with response to the compound (see Section 7.6.1.).

Pharmacokinetic Assessment

The levels of sprifermin/FGF-18 in serum will be assessed 2 hours after the last dose of each cycle and will give an indication of whether sprifermin reaches the systemic circulation. Based on previous trials, systemic levels of sprifermin/FGF-18 are expected to be below the LLOQ.

Levels of sprifermin/FGF-18 in synovial fluid will be measured in order to give a first estimate of the residence time of sprifermin in the synovial fluid.

Evaluation of Health-related Quality of Life

The KOOS (see Section 7.7.1) is a knee-specific questionnaire designed to evaluate both short-term and long-term consequences of knee injury, including OA; it is intended for use in knee injury potentially leading to post-traumatic OA or in primary OA. The KOOS QOL subscale is more specific to QOL in subjects with knee OA than the more general MOS SF-36 (see below), and may better predict future need for knee replacement.

The MOS SF-36 (see Section 7.7.2) is a generic patient-reported health-related QOL instrument that is widely used in different diseases and conditions (including OA). MOS SF-36 results from this trial will be used to determine whether the MOS SF-36 is sensitive enough to measure changes in QOL in the trial population.

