- Change from baseline in serum, urine, and synovial markers associated with administration of the compound
- Baseline biochemical biomarkers and/or genetic markers associated with response to treatment or disease progression (response assessed by MRI, X-ray and/or questionnaire)
- Changes in MRI outcomes, WOMAC scores, 20-meter walk test, PGA, PGIC, JSW, OMERACT-OARSI responder rate, KOOS QOL, KOOS Symptom Index, MOS SF-36, NRS pain score in the target and contralateral knee, presence of pain in other joints, ICOAP, safety laboratory values, and vital signs over the extended follow-up period and nature, incidence and severity of local and systemic AEs during the extended follow-up period (to be summarized descriptively)
- Relationship between dosing (dose and regimen), cartilage structures, and clinical scores as a function of time

Trial Design	This is a multicenter, randomized, double-blind, placebo-controlled, parallel-group Phase II trial of sprifermin administered i.a. in subjects with primary OA of the knee and Kellgren-Lawrence (KL) grade 2 or 3.
	The trial consists of a screening period lasting up to 42 days, a 2-year (104-week) double-blind placebo-controlled (DBPC) treatment phase, which will start at randomization (Week 0/Visit 2) and a 3-year extended follow-up phase. Please see table 5 and 6 (Appendix E) in the clinical trial protocol. Please see below for specification of dose groups (Trial Product).
Number of Subjects	The trial will randomize approximately 545 subjects (109 per treatment group).
Trial Product	Sprifermin (also known as: recombinant human fibroblast growth factor 18 [rhFGF-18]; AS902330) 30 mcg or 100 mcg, administered intra-articularly (i.a.).
	Subjects will receive 4 cycles of treatment (each consisting of 3 once-weekly i.a. injections over 3 consecutive weeks) at intervals of 6 months.
	Subjects will be randomized in equal allocation to one of 5 treatment groups:
	• 4 cycles of sprifermin (100 mcg per injection, total dose 1200 mcg)
	• 2 cycles of sprifermin (100 mcg per injection) alternating with 2 cycles of placebo (total dose 600 mcg)
	• 4 cycles of sprifermin (30 mcg per injection, total dose 360 mcg)
	• 2 cycles of sprifermin (30 mcg per injection) alternating with 2 cycles of placebo (total dose 180 mcg)
	• 4 cycles of placebo (total dose 0 mcg)
Treatment and Trial Duration	Planned treatment duration is 2 years.
	Follow-up duration is 3 years.

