that the database can be partially locked, then the database will be partially locked, the treatment code will be un-blinded, complete analyses of the DBPC phase will be performed. All data that is collected until week 104 (day 819:see table 3 for definition of target day and allowed windows) will be included in the statistical analysis of the partially locked database for the DBPC treatment phase. Each dataset will include variable to flag if a record will be included in analyses for the DBPC treatment phase. If records belong to days \geq 820 they will be part of the long term follow-up analysis. Further description of database lock handling appears in the Data Management plan. The SAP has to be approved prior to database partial lock and breaking the blind. This will be referred to as 2-year analysis.

• Long term follow-up data will be analyzed and reported in addition to the DBPC treatment phase results. This will be referred to as 5-year analysis and will include data from baseline (baseline, day 1) until end of extended follow-up period (Year 5). To minimize bias during the extended follow-up phase, all site staff including Investigators, study monitors, X-ray and MRI readers, and subjects will remain blinded during the extended follow-up phase. Subjects will maintain their subject number from treatment phase to follow-up. X-ray and MRI readers will remain blinded during the study and after the study completion.

Study Design

• In addition, a Year-3 analysis, repeating Year-2 analysis for primary and secondary efficacy endpoints as well as safety endpoints is planned.

No interim analysis is planned before the primary analysis defined at 2 years; however, an Independent Data Monitoring Committee (IDMC) will perform periodic reviews of semi-unblinded data to evaluate the safety of the subjects on an ongoing basis. Detailed description of the safety monitoring is specified in a dedicated IDMC charter [2].

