8.2 Analysis of data from the follow-up phase

An overview of endpoints and type of analysis for the follow-up phase is provided in Appendix 19.1. In general, the same endpoints (for efficacy and safety) will be presented as for the treatment phase and the analysis of follow-up period (up to week 260) will be integrated combining all available data in the entire 5 years period (including data from the DBPC). No multiplicity adjustment for the integrated analysis will be done, as the efficacy evaluation on the integrated data is considered exploratory.

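### The plan names adverse events during the extended follow-up as an endpoint, but for the 5-year analysis it specifies only a pooled whole-study summary and no summary by follow-up onset

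*SAP*

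**What the plan says.** Protocol 8.3.4 and SAP Section 6 (Trial Endpoints, Exploratory) both include "nature, incidence and severity of local and systemic AEs during the extended follow-up period (to be summarized descriptively" as an endpoint. Protocol 5.2 gives the purpose: "The extension phase of the trial will allow exploration of the drug's long-term safety".

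SAP 17.1 sets the rule for the 5-year analysis: "All AEs from the complete duration of the study will be summarized", and "There will be no summaries of TEAEs for the 5 years analysis only AE". This agrees with SAP 8.2, where the follow-up analysis "will be integrated combining all available data in the entire 5 years period (including data from the DBPC", and with Appendix 19.1, whose follow-up column is headed as integrated and runs from baseline to LOCF2.

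SAP 17.1.1 reports numbers and percentages of subjects. Its tables by local/systemic class, severity and relationship are defined for TEAEs, and its three special-interest tables (injection site reactions, musculoskeletal disorders, neoplasms) are labelled treatment-emergent. The tables not so limited are the overview, all serious AEs, and non-serious AEs reaching 5% in any group. In 17.2.2 the local, systemic and relationship tables for serious AEs are again treatment-emergent. The key safety outputs in Appendix 19.5.3 include no table by follow-up onset.

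**The concern.** An endpoint defined on one phase needs a summary of that phase. As written, the reader of the 5-year report gets a cumulative percentage over treatment and follow-up together. That figure cannot show whether AEs arising after treatment differ between arms, which is what the extension is meant to explore. The classes the endpoint names, local versus systemic and severity, are the ones whose tables are tied to the treatment-emergent window.

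What is at stake is the interpretability of the long-term safety description, not the 2-year efficacy conclusions.

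**Working it through.** The documents give no AE rates, so there is no stated figure to reproduce. The check has two parts.

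**1. What the treatment-emergent tables cover.** Inputs: last injection at Week 80 (Protocol 6.2, Table 1); TEAE window to 30 days after last injection (SAP 17.1); treatment-phase data cut at day 819 (SAP Section 8); Week 260 target day 1821 (SAP Table 3). For a subject dosed on schedule:

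- Last injection: 80 × 7 + 1 = day 561.
- End of TEAE window: 561 + 30 = day 591.
- Between TEAE window and data cut: days 592 to 819, that is 819 − 591 = 228 days.
- After the data cut to Week 260: days 820 to 1821, that is 1821 − 819 = 1002 days, or 1002/1821 = 55% of planned time.
- Outside the TEAE window altogether: (1821 − 591)/1821 = 1230/1821 = 68%.

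So for about two-thirds of planned time, the tables as listed in 17.1.1 give no breakdown by local/systemic class, severity, relationship or special interest.

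**2. What pooling does to a difference in follow-up.** Let p1 be the incidence of a category in the treatment phase, equal in both arms, and p2 its incidence in follow-up. Assume independence. Counting each subject once gives a pooled incidence of 1 − (1 − p1)(1 − p2). All rates are assumptions. With p2 = 10% versus 20%:

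| p1 | Pooled, arm A | Pooled, arm B | Difference | Ratio |
|---|---|---|---|---|
| 0% | 10% | 20% | 10 points | 2.00 |
| 30% | 37% | 44% | 7 points | 1.19 |
| 50% | 55% | 60% | 5 points | 1.09 |
| 70% | 73% | 76% | 3 points | 1.04 |

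For example, at p1 = 50%: 1 − 0.5 × 0.9 = 0.55 and 1 − 0.5 × 0.8 = 0.60.

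Now let only a fraction r enter follow-up while the denominator stays at all treated subjects. The pooled incidence is p1 + (1 − p1) × r × p2. Take r = 0.7, from the planned 30% drop-out (Protocol 8.1), and a rarer event with p2 = 3% versus 10%:

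| p1 | Pooled, arm A | Pooled, arm B | Ratio |
|---|---|---|---|
| 0% | 2.1% | 7.0% | 3.3 |
| 10% | 11.9% | 16.3% | 1.37 |
| 20% | 21.7% | 25.6% | 1.18 |
| 40% | 41.3% | 44.2% | 1.07 |

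A follow-up-only table among subjects who entered follow-up would show 3% versus 10%, a ratio of 3.3, in every row. Dilution therefore depends on how common the term was during treatment. For a term absent during treatment the ratio is unchanged.

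**The case against.** The strongest reply is that the SAP already holds most of what is needed. Section 8 assigns records from day 820 to the long-term analysis and requires a flag for treatment-phase records. Appendix 19.4 derives a post-treatment AE class. Section 17.1.1 plans a listing of all AEs with onset date, severity and relationship. Section 8.2 says that in general the same endpoints will be presented as for the treatment phase, so the 17.1.1 tables may be meant to be rerun on all AEs at Year 5. Section 17.1 also describes the special-interest groups without limiting them to treatment-emergent events. All of this stands, but it does not supply the summary. Rerun tables would still be pooled, and a listing is not a descriptive summary. The listing's stated contents also omit the local/systemic class that Protocol 7.4.1.2 has investigators record. The Year-3 analysis repeats the Year-2 one, so for subjects dosed on schedule its TEAE tables would add no follow-up events.

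Four stronger readings are tempting, and the documents do not support them.

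- A reader might infer that the pooled table starts at consent. Section 8 says the 5-year analysis "will include data from baseline (baseline, day 1) until end of extended follow-up period (Year 5", and 17.1 says AEs "starting between date of informed consent and until date of first dose of study treatment will be tabulated separately". The wording in 17.1 about the whole study is only loose.
- A reader might infer that the follow-up endpoint will never be produced. The table shells are a separate document, declared an integral part of the SAP (Section 19), and were not available. All that can be said is that the SAP text specifies no such summary.
- A reader might infer that late signals are masked. A term first seen in follow-up still shows, and because 17.1.1 takes the worst severity, a more severe late event is not simply lost.
- A reader might infer five-fold weaker AE ascertainment after Week 104, from 21 visits in 2 years against 6 in 3 years. Sixteen of the 21 visits fall in the four injection cycles; outside them the gaps are 9 and 14 weeks, against 26 in follow-up. AEs are recorded continuously and by diary in both phases, on the same schedule in every arm. The visit pattern is a reason not to compare rates between phases, and no more than that.

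**Conclusion.** The point holds as a gap between a named endpoint and its specified analysis. Following the SAP text as written yields a whole-study summary and no AE summary by follow-up onset. The cost is dilution of between-arm differences for terms common on treatment: a 10-point, two-fold difference becomes 7, 5 or 3 points at 30%, 50% or 70% prior incidence. These sizes rest on assumed rates, equal treatment-phase incidence across arms, and independence between phases. Equal drop-out across arms would shrink the follow-up contribution but leave its ratio unchanged.

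The endpoint is exploratory and descriptive, so this is an inexpensive improvement and not a threat to the trial's main conclusions.

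**What to change.** In SAP 17.1 and 17.1.1, keep the pooled 5-year table and add the AE tables (overall, local, systemic, severity, relationship, serious, special interest) by onset period:

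1. the TEAE window;
2. more than 30 days after last dose, through day 819;
3. day 820 onward.

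The middle period is needed because a cut at day 820 alone would leave AEs starting on about days 592 to 819 in neither the TEAE tables nor the follow-up ones. It also covers subjects who stop treatment early, since it is defined from each subject's last dose.

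For the third period, use subjects observed after day 819 as the denominator and show n, percentage, subject-years and events per subject-year by arm. State that arms are compared within a period only. Align the wording in 17.1 on the whole study with the day-1 start in Section 8.

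The cost is one extra set of descriptive tables from data already collected, with a cut the SAP already defines. The limitation is that the follow-up tables describe only subjects who stayed, which is why subject-years by arm should be shown.
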